#### **Exclusion criteria**

- 1) Current diagnosis of an additional neurologic condition such as multiple sclerosis, Parkinson's disease, stroke, or brain injury
- Presence of unstable or uncontrolled medical conditions such as cardiovascular disease, myocardial infarction (<1 year), pulmonary infection or illness, renal disease, autonomic dysreflexia, infections, pain, heterotopic ossification
- 3) Cognitive or communication impairments limiting communication with study staff or ability to provide informed consent
- Lower extremity joint contractures limiting the ability to stand upright and practice walking
- 5) Skin lesions or wounds affecting participation in walking rehabilitation
- 6) Acute or unstable fracture, diagnosis of osteoarthritis or bone impairments affecting safe participation in walking rehabilitation
- Severe spasticity or uncontrolled movements limiting participation in walking rehabilitation
- 8) Body weight or height that is incompatible with safe use of a support harness and body weight support system
- 9) Pain that limits walking or participation in walking rehabilitation
- 10) Current participation in rehabilitation to address walking function
- 11)Botox injections in lower extremity muscles affecting walking function within 4 months of study enrollment
- 12)Legal blindness or severe visual impairment
- 13)Known pregnancy
- 14) Implanted metal hardware of the spine below the 8th thoracic vertebrae

At the discretion of the Principal Investigator, any individual may be deemed ineligible for further participation in this study if there are concerns about the individual's capability to perform study procedures or if it may be unsafe for the volunteer to participate in the study. Furthermore, minor exceptions to the inclusion/exclusion criteria may be permitted at the discretion of the Principal Investigator if those exceptions do not influence participant safety. For example, a small deviation from the requirement for the participant to walking 10 feet with minimal assistance (i.e. able to walk 8 feet) may be permitted if they demonstrate the capacity to complete the testing and training. This is important to ensure that individuals are not excluded for insignificant reasons and to facilitate meeting enrollment benchmarks.

# Step one-phone screening

Once a potential participant makes contact with study staff through one of the above-mentioned means, an IRB-approved phone script and screening form will be used to guide the phone screening process (see Recruitment Attachments for phone screening script). Depending on preference, we can also conduct this screening in person. The screening form, designed to avoid collection of protected health information, will ask subjects general information about their eligibility. This information may include health status, physical functioning, history of neurologic impairments, the date of their SCI, movement and sensory impairments, other secondary medical conditions and other information pertaining to inclusion/exclusion criteria. If any potential participant is deemed ineligible for the study during this or a later step of the screening process, all study documentation that had been collected regarding the individual will be destroyed. If an individual passes step one of the screening process and would like to continue with the screening process, participants will be informed of the on-site screening (step two) and medical screening (step three) processes.

# Step two- on-site screening

Participants will be asked to come to Brooks Rehabilitation for the on-site screening. At the beginning of this visit, informed consent will be obtained, using the ICF-Screening form for guidance, to inform the individual of the purpose, procedures, possible benefits/risks, alternative to the screening process, and how the individual's protected health information will be collected, used, and shared with others. The potential participant will have the opportunity to review the ICF-Screening and a study staff member will be available to answer questions. We anticipate that some potential participants may want to meet with study staff ahead of time to discuss the screening and study procedures. If so, the informed consent process for the screening may occur on a separate day based on the preference of the potential participant.

The screening will involve clinical tests of motor function (i.e. clinical tests of strength) and functional mobility tasks such as standing and walking. The potential participant will be asked about any conditions of pain and we will confirm any details pertaining to their health and functioning to verify their ability to perform locomotor training (condition of skin, range of motion, spasticity). The following tests, or portions of them, may be used to objectively measure the participant's status and confirm eligibility for enrollment:

- International Standards for the Neurological Classification of Spinal Cord Injury (INSCI) examination- The ISNCSCI is a standardized assessment used to determine the motor and sensory impairment and severity of a spinal cord injury (previously known as the ASIA examination based on the American Spinal Injury Association).
- Spinal Cord Assessment Tool for Spastic Reflexes (SCATS)- The SCATS is a reliable and valid tool for assessing spasm activity of flexor and extensor muscle groups as well as spastic hypertonia in patients with spinal cord injury.
- Brief Pain Inventory (BPI)- This validated self-report questionnaire assesses pain severity and its impact on function. The BPI items are a more comprehensive measure of pain interference compared to some other measures in the SCI population.
- 10-Meter Walk Test (10MWT)- This validated measures assesses forward walking speed.
- Vital signs- To assess participant safety and responses to study procedures, we will monitor blood pressure, heart rate, respiratory rate and pulse oximetry during study procedures. Establishment of baseline readings and monitoring of cardiopulmonary responses will allow for assessment of abnormal responses such as autonomic dysreflexia.

Female subjects of potential childbearing age will be asked to take a pregnancy test. Furthermore, participants will be instructed that they should take precautions against becoming pregnant during the study because the fetal risks associated with tsDCS are unknown. If a participant learns that she is pregnant, she must withdraw from the study immediately. All test outcomes will be recorded on the On-Site Screening Form (see Information Sources and Identifier attachments). If participants complete the on-site screening, are deemed eligible and wish to pursue enrollment in the study, the participant will proceed to the medical screening step. They will also be provided with the informed consent form for the full study (ICF- Intervention) so that they may review this information ahead of time.

## Step three- medical screening and physician approval

[figure not shown]
Medical records will be obtained using the Medical Record Authorization form (see Information Sources and Identifier attachments). This form will be provided to the potential participant requesting their date of birth and signature to allow release of their medical records. Once the records are received, study staff will perform a medical record screen using the Medical Record Screening Form (see Information Sources and Identifier attachments) to verify the potential participant meets enrollment criteria. The study physician will oversee this process. In addition to the medical record screen, a written confirmation of medical approval by a physician, using the IRB-approved Physician Approval Letter/Form (see Information Sources and Identifier attachments), also will be required to indicate the potential participant is medically safe to participate in study procedures and does not have known medical conditions that violate the enrollment criteria.

If an individual completes and passes all three steps of the screening process, the participant can then choose to enroll in the full study. The informed consent form (ICF-Intervention) will be provided at the completion of the screening visit to allow potential participants to time to review the document in advance. Generally, the individual will be informed of the study purpose, procedures, possible benefits/risks, the alternatives to being in the study and how the individual's protected health information will be collected, used, and shared with others using the ICF-Intervention as a guide. Participants can either complete the informed consent and begin study procedures on the same day or study staff will schedule a separate time for the individual to complete the informed consent and enroll in the study.

## Study Procedures Overview

For Aim 1 (immediate effects of tsDCS), participants will complete two separate testing sessions, presented in random order, that involve up to 30 minutes of tsDCS at one of the two dosages while walking. We will assess changes in muscle activity, kinematics and spinal excitability before and at the end of the period of walking. The two sessions will last about 3 hours and no longer than 6 hours and will take place at least 48 hours apart to allow for wash-out of stimulation effects.

For Aim 2 (effects of tsDCS applied with locomotor training), participants will be randomized to receive 16 sessions of locomotor training with tsDCS at one of the two dosages. Each intervention session will last about 1 hour and no longer than 2.5 hours. Before and after the 16-session intervention (i.e., at baseline and post intervention), we will assess functional outcomes through standardized clinical tests of walking speed and endurance, as well as changes in muscle activity, kinematics and spinal excitability. We will also examine the participant's spasticity and pain using standardized assessments. Each assessment session will last about 3 hours and no longer than 6 hours.

Overall, the testing and intervention procedures of this study will be as follows (see Fig. 1 for details):

- 1. Aim 1's first visit will consist of clinical testing and collection of basic demographic information (see Information Sources and Identifier attachments for demographics form) to characterize the participant. Neuromechanical assessments of walking and reflex testing prior to and after 30 minutes of tsDCS at one of the two dosages delivered while walking on a treadmill will be conducted.
- 2. Aim 1's second visit will involve identical procedures for stimulation and neuromechanical assessments as compared to visit 1 except for crossover of the tsDCS dosage. It will also include any clinical testing not completed on day 1.
- 3. Aim 2's pre-test will consist of neuromechanical assessments of walking and reflex testing as well as clinical assessments of pain, spasticity, and physical function.
- 4. 16 sessions of locomotor training will be conducted over 4 weeks with one of the two dosages of tsDCS applied during the training.
- 5. Aim 2's post-test will repeat the measures completed at pre-test.

A physical therapist will oversee study procedures. Vital signs, such as blood pressure, heart rate and blood oxygen saturation, will be monitored for safety. Rest breaks will be provided at regular intervals and at any time the participant requests. Participants will be informed that they may choose not to perform any aspect of the study. We will adjust the assessment protocol, outlined below, as needed in response to our participants, such as reducing the assessments due to fatigue or individual tolerance.

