#### 6. Research Plan:

#### Recruitment

A minimum of eight individuals are required to complete this pilot study. We aim to screen 30 individuals and enroll 20 subjects in this study. The target population will be

individuals with SCI. Study procedures will take place at Brooks Rehabilitation, which includes a clinical research facility directed by [name] (Principal Investigator). Potential participants will learn about the study and be recruited in the following primary ways:

- Local advertisements or study flyers (see Recruitment Methods attachments
  for study flyer and email script for potential participants). Individuals may
  contact study personnel at Brooks Rehabilitation. Study staff will be available
  to answer any questions and if the potential participant is interested, the
  individual will be screened for eligibility (screening process detailed below).
- 2. Health care providers at Brooks Rehabilitation or other clinics in the north Florida area (e.g. physicians, physical therapists, or occupational therapists) (see Recruitment Methods attachments for email script for healthcare providers). Health care providers may ask potential participants if they would like to learn more about a current research study. If interested, the potential participants will be provided with a flyer, which will contain instructions for contacting the study staff at the Brooks Rehabilitation Motion Analysis Center. Study staff will be available to answer any questions and if the potential participant is interested, the individual will be screened for eligibility.
- 3. Additionally, the health care provider may ask the potential participant if they are interested in being contacted by a study staff member regarding this research study (see Recruitment Methods attachments for authorization to release patient information form). If written authorization is provided by the potential participant, the health care provider will request his/her name, telephone number, and email address in order to be contacted by the study staff directly. This recruitment strategy will be necessary to help facilitate communication between the potential participant and the study staff. Study staff will contact the potential participant and answer any questions. If the potential participant is interested, the individual will be screened for eligibility.

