## Neuromechanical assessments of walking

Neuromechanical assessments, such as the analysis of muscle activation and movement during walking, will be conducted during testing for both Aim 1 and 2. During Aim 1, the assessments will occur before and after the completion of up to 30 minutes of treadmill walking. As most participants will not tolerate 30 minutes of uninterrupted walking, the session will be divided with rest breaks as needed to deliver a total of ~30 minutes of walking. tsDCS at one of the two dosages will be applied for up to 30 minutes. The goal of the protocol is to complete 30 minutes of walking with stimulation. However, we recognize that this protocol may need to be adjusted slightly for some individuals based on aspects such as comfort or fatigue. During Aim 2, neuromechanical assessments of walking will be conducted before and after the 16 sessions of locomotor training. To perform these neuromechanical assessments, participants may be asked to perform activities such as treadmill walking or overground walking at self-selected or fastest-comfortable walking speeds, walking backward, and stepping over an obstacle. Participants may use any typically used orthotics (i.e. AFOs) or gait assistive devices required by the participant.

All testing procedures will be closely monitored by a physical therapist who will monitor the participant's vital signs for safety and provide rest breaks as needed or requested. A safety harness attached to an overhead support system may be used when performing walking overground. Testing will also occur while walking on a treadmill using a harness to secure the participant to an overhead support system to provide partial body weight support if needed. Participants may opt not to perform any walking task, and all tasks will be adjusted for each participant's functional level. Study procedures will be explained ahead of time and participants will be asked to wear appropriate clothing for participation. Participants will be able to sit comfortably during the set-up procedures. During the set-

[figure not shown]
up, small reflective markers and EMG sensors will be affixed to the skin and will be removed at the conclusion of the assessment (details below).

The following procedures will be completed during the neuromechanical assessments:

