## Locomotor training

Participants will be randomized to either the combined intervention of higher dosage tsDCS with locomotor training or lower dosage tsDCS with locomotor training. Each participant will receive up to 16 sessions of training with each session including up to 40 minutes of walking. The goal is to have participants attend 4 sessions per week for 4 weeks, but the individual schedules might vary. All sessions will be led by a licensed physical therapist with experience in walking rehabilitation after ISCI. There will be two components to the locomotor training session: 1) body-weight supported treadmill locomotor training with tsDCS (LT-TM) and 2) overground walking without tsDCS (OG).

1) LT-TM (30 min): This portion of the intervention will consist of 30 minutes of locomotor training on a treadmill and will follow standard procedures for body-weight supported treadmill locomotor training that have been published by our group and others. tsDCS, as described above, will be applied during body-weight supported treadmill locomotor training. Briefly, participants will walk on a treadmill with verbal feedback and manual assistance provided by training staff. This assistance is provided as needed to help move the leg during stepping and/or to maintain stability and balance. Avoidance of falls is assured while walking on the treadmill by an overhead body weight support safety attached to a trunk/pelvis harness. Body weight support will be set low as possible in order to allow balance responses and to afford support only as needed. Performance without compensation strategies (hip hiking, leaning to one side) will be emphasized. Rest breaks will be provided as needed.

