## Statistical Plan

A descriptive analysis of demographic data and injury characteristics will be conducted using a frequency distribution for categorical data and means for continuous variables. These data will be used to characterize general information about the study population. Sample size and data distribution will guide statistical analysis. If data assumptions are achieved, for Aim 1, we will determine the effects of tsDCS during walking using two-way repeated measures ANOVAs. The within factors will be time (before or at the end of walking bout) and stimulation (higher or lower dosage tsDCS). We will then examine the interaction effect to determine differences in the changes during walking with the two dosages of tsDCS. For Aim 2, mixed method ANOVAs will be used to determine the effects of tsDCS dosage during locomotor training. The within factor will be time (pre- or post-test) and between factor will be group (higher or lower dosage tsDCS). We will then examine the interaction effect to determine differences in the improvement during locomotor training with the two dosages of tsDCS. Differences will be considered significant at p<.05. Data will be analyzed using professional statistical software.

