# Safety monitoring

Although numerous studies indicate tsDCS is easily tolerated and no adverse responses have been reported, 15,51 we will closely monitor participant responses. At each session the participant and physical therapist will complete a questionnaire to document any side effects such as stimulation site discomfort or skin irritation. While we do not expect any issues, we will monitor the skin closely. If any changes are observed beyond mild redness or if persistent discomfort is reported, stimulation intensity will be reduced (or discontinued, if necessary) during that training session and increased to 2.5mA in subsequent sessions if tolerated. Irritation could also occur if the harness is not fitted or positioned correctly, so this will be closely monitored and adjustments will be made as needed. In accordance with University of Florida IRB policy, adverse events that are both unexpected and serious will be reported within 5 working days.

The testing and intervention procedures could be tiring for some individuals. All participants will be given rest breaks and informed that they may rest or terminate their participation at any time. Blood pressure (BP) and heart rate (HR) will be monitored during each testing and intervention session. BP and HR must be within a medically-acceptable range for the participant to participate in a testing or training session. Resting diastolic BP must be less than 100mmHg to begin the session. The criteria for termination include complaints or symptoms of confusion, dyspnea, onset of angina, excessive blood pressure changes (systolic BP greater than 200mmHg or diastolic BP greater than 110mmHg). In addition, should the participant's HR exceed 85% of the predicted maximum HR or the participant reports a Borg rating of perceived exertion (RPE) rate of greater than 17/20, then the session will be slowed and/or halted. If the session is halted,

the participant will be asked to rest while BP and HR are monitored and will resume only when BP and HR return to acceptable values and the participant reports no other symptoms. If any of these conditions persist after rest, the participant's primary physician and/or the study physician may be contacted and the participant may be referred for evaluation. If the participant complains of angina at rest, loss of consciousness occurs, or cardiac arrest, emergency medical services through 911 will be called immediately.

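### The plan does not say whether Aim 2 participants who stop training early are post-tested, so the randomised comparison of walking speed and endurance may become a comparison of completers

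*Combined protocol and SAP*

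**What the plan says.** All sections named here are in the combined protocol and SAP.

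- **Timing of the post-test.** Study Procedures Overview: "Before and after the 16-session intervention (i.e., at baseline and post intervention), we will assess functional outcomes through standardized clinical tests of walking speed". Neuromechanical assessments of walking: "During Aim 2, neuromechanical assessments of walking will be conducted before and after the 16 sessions of locomotor training". Neither place gives a date or window counted from the pre-test or from randomisation. Specific Aims names walking speed and endurance as the primary functional outcomes of Aim 2.
- **Length of the course.** Locomotor training: "Each participant will receive up to 16 sessions of training with each session including up to 40 minutes of walking". Four sessions a week for four weeks is a goal, and individual schedules may differ.
- **Leaving for good.** Step two (on-site screening): "If a participant learns that she is pregnant, she must withdraw from the study immediately". Safety monitoring: "All participants will be given rest breaks and informed that they may rest or terminate their participation at any time". The discretion paragraph after the exclusion criteria lets the principal investigator rule a person out of continuing. None of these mentions a post-test.
- **Staying with less treatment.** Safety monitoring lets stimulation be lowered or switched off within a session and raised again later. Study Procedures Overview lets participants decline individual parts.
- **Analysis.** The Statistical Plan uses a mixed ANOVA for Aim 2, read through its interaction: "The within factor will be time (pre- or post-test) and between factor will be group (higher or lower dosage tsDCS". It names no analysis set, no rule to analyse by assigned group and no handling of a missing post-test.

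**The concern.** Someone who stops training permanently has no scheduled point at which walking is measured again. Staff would have to decide case by case whether to bring that person back. Without a post-test the person has no change score and contributes nothing to the interaction test.

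Randomisation protects the comparison of everyone randomised. It does not protect a comparison of those who happened to finish. The arms differ in a way that could affect stopping: the higher dosage is sustained current of up to 2.5 mA, while the lower is given only as 30-second ramps at the start and end (Delivery of tsDCS). Safety monitoring anticipates stimulation-site discomfort and skin irritation. The risks section anticipates fatigue, which could be related to walking progress. Stopping that differs by arm and is related to outcome is therefore plausible, although the documents give no rate for it. A post-test that was never done cannot be recovered at analysis.

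**Working it through.** **Reproducing the plan's figures.** Recruitment gives a minimum of 8 and an enrolment aim of 20, with no effect size, SD, power or dropout rate. There is nothing to reproduce, so all sizes below are illustrations.

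**Assumptions.** 10 per arm (20 enrolled, equal allocation; no ratio is stated), two-sided 5% level (sidedness is not stated), change scores with SD 1, no true effect. With two arms and two time points, the time-by-group interaction is the same test as a two-sample t-test on pre-to-post change.

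**Step 1: chance that the question arises.** P(at least one stopper among 20) = 1 − (1 − q)^20. At assumed stop rates q of 5%, 10% and 20% this is 64%, 88% and 99%.

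**Step 2: bias with a fixed number of stoppers in one arm.** Let k of 10 in one arm stop, those lowest on a score that correlates r with change. The completers' mean in that arm rises by r × S_k / (10 − k), where S_k is the absolute sum of the k lowest expected normal order statistics in a sample of 10.

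- k = 2, S_2 = 2.54: 2.54 / 8 = 0.32 SD at r = 1, and 0.5 × 0.32 = 0.16 SD at r = 0.5.
- k = 3, S_3 = 3.20: 3.20 / 7 = 0.46 SD at r = 1, and 0.23 SD at r = 0.5.

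A simulation of 100,000 trials gave the same biases to within 0.01 SD. For k = 2 the false-positive rate was 6.5% at r = 0.5 and 11.6% at r = 1, against a nominal 5%.

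**Step 3: cross-check with stop rates instead of counts.** The bias per arm is r × φ(z_q) / (1 − q), and the contrast is the difference between arms.

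| Stopping, one arm / other arm | r = 0.5 | r = 1 |
|---|---|---|
| 20% / 0% | 0.17 SD | 0.35 SD |
| 30% / 10% | 0.15 SD | 0.30 SD |
| 20% / 20% | 0 | 0 |

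The last row is the balanced case: equal stopping for the same reasons gives no bias.

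**Step 4: cost in precision.** By noncentral t, the difference detectable with 80% power is 1.33 SD of change at 10 per arm, 1.51 SD at 8 per arm and 1.64 SD at 7 per arm. Balanced losses still reduce what a small study can show.

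**The case against.** The strongest reply is that no text excludes early stoppers. The course is defined as a maximum of 16 sessions on a flexible schedule, so a post-test after a shortened course fits the wording. Safety monitoring deals with discomfort by adjusting stimulation while the participant carries on, which weakens the most obvious route to arm-related dropout. The same section says tsDCS is well tolerated, and Delivery of tsDCS says the two dosages have been reported to feel alike. At r = 0.5 with 2 stoppers, the 0.16 SD bias is about a third of the standard error, √(1/10 + 1/8) = 0.47.

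Much of this stands and limits the point. Three stronger readings are tempting and are not supported:

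- A reader might infer that the plan bars early stoppers from the post-test. It is silent; their loss is an inference from that silence.
- A reader might infer that stopping stimulation always means leaving the study. The within-session adjustment and the freedom to decline parts say otherwise. They do not, however, cover someone who stops training for good.
- From "A minimum of eight individuals are required to complete this pilot study" and the aim of 20, a reader might infer that 12 of 20 may be lost after randomisation. The minimum concerns the whole pilot, including the Aim 1 crossover, and losses before Aim 2 randomisation do not affect the randomised contrast.

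Nor do the documents show which arm would gain: discomfort need not be related to walking change.

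Fig. 1, to which Study Procedures Overview refers for details, is not shown, and the consent pages were removed. Both should be checked before acting.

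**Conclusion.** The point holds as a gap with a real but conditional consequence. The readable text ties the Aim 2 post-test to the end of the course, describes permanent exits as leaving the study, and plans an analysis that in standard form needs both values. Following it can turn the randomised comparison of walking speed and endurance into a completer comparison; it need not do so.

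The illustrative bias is about 0.16 SD of change (2 stoppers in one arm, correlation 0.5), up to 0.32 SD if the two poorest responders are the ones who stop. Arm size, stopper counts and correlations are all assumed, and the larger figure is an extreme. Where both arms lose people equally for the same reasons, the cost is mainly precision. The change is worth making before enrolment because the remedy lies in data collection and cannot be supplied later.

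**What to change.** 1. In Study Procedures Overview, Locomotor training and Safety monitoring, distinguish permanently stopping tsDCS or training from withdrawing consent for follow-up.
2. Invite every randomised participant who has not withdrawn consent to the existing post-test, whatever number of sessions was attended. Hold it at the end of the participant's course or, for an early stopper, at about the time the planned course would have ended. This keeps the flexible schedules and avoids testing slower participants in mid-course.
3. In the Statistical Plan, analyse participants in the dosage group assigned and state how post-tests that are still missing will be handled.
4. Record the number of sessions attended and the reason for stopping.

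The pregnancy withdrawal rule in Step two is left to the sponsor; nothing here proposes changing it.

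The cost is protocol and consent wording. The post-test visit and its $20 payment are already planned (Financial). The downside is a slightly diluted expected effect, because people who trained less are included, and some stoppers will decline to return.
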